#### 4.5 Dose-Limiting Toxicity

Dose-limiting toxicities will be determined during the first four weeks/28 days (first cycle) of Treatment Period 2 (Cohorts 1-4) or during Cycle 1 (Cohort 5 and all subsequent cohorts). A DLT is defined by the occurrence of any of the following toxicities related to ARQ 087 within the first 28 days of continuous treatment (Treatment Period 2 or Cycle 1 of Continuous Dosing) and graded according to the Common Terminology Criteria for Adverse Events (CTCAE) version 4.03:

- Grade 4 anemia
- Grade 4 neutropenia
- Grade 4 thrombocytopenia
- Grade 3 neutropenia with fever ( $\geq 38^{\circ}\text{C}/100.4^{\circ}\text{F}$ )
- Grade 3 neutropenia lasting longer than 7 days despite optimal treatment
- Grade 3 thrombocytopenia in the presence of bleeding
- $\geq$  Grade 3 hyperglycemia (fasting blood glucose  $> 250$  mg/dL or non-fasting  $> 500$  mg/dL) requiring insulin (uncontrolled with metformin)
- $\geq$  Grade 3 non-hematological toxicity of any duration, except for the following:
  - Nausea, vomiting, or diarrhea responding to optimal medical management within 48 hours
  - Alopecia
- Any other toxicity that in the view of the Investigator represents a clinically significant hazard to the subject

**Note:** During the dose escalation phase, if the subject experienced a DLT, such subject should be permanently discontinued from the treatment.

#### **4.6 Study Duration**

Subjects will receive treatment with ARQ 087 until progression of disease (clinical or radiological), unacceptable toxicity, or another of the discontinuation criterion is met (see Section 5.8). It is expected that most subjects will receive between one and six cycles of ARQ 087 for a treatment period of four to 24 weeks.

## 5 STUDY VISITS

Before the start of any study required procedures, the Investigator or designee must obtain a signed written informed consent form (ICF) for the study from each prospective study subject or his/her legal representative.

Study visits will consist of Pre-study Visit(s), during which the subject's eligibility for the study and baseline disease state will be evaluated; four Daily Visits during Treatment Period 1 (Cohorts 1-4); four Weekly Visits during Cycle 1; and Bi-weekly Visits thereafter (Cycle 2+) during which the subject will be evaluated. Additionally, an End of Treatment Visit(s) and 30-day Safety Follow-up(s) Visit will be performed (see Appendix 1 for the Schedule of Assessments).

Following the Pre-study evaluation and a determination by the Investigator and ArQule's Medical Monitor that the subject meets all inclusion/exclusion criteria, the subject will be considered entered into the study.

### 5.1 Informed Consent

A sample ICF with core information will be provided to each study site. Prior to study initiation at a given study site, each site/Investigator must obtain a written approval/favorable opinion from its respective IRB/IEC for the ICF and any other written information to be provided to subjects. All ICFs must be compliant with International Conference on Harmonization (ICH) GCP guidelines, and local regulations and must be approved by the Sponsor prior to submission to IRB/IEC. The written approval of the IRB/IEC, together with the approved subject information/ICF, must be maintained in the study master files.

Written informed consent must be obtained from a prospective subject before any study-specific procedures are performed on that individual. Subjects who agree to participate in the study will sign the most recently approved ICF and will be provided with a copy of the fully executed document. The original, executed ICF will be maintained in the respective subject's clinical study file.

### 5.2 Pre-Study Evaluations (Baseline) (Within 21 Days Prior to the First Dose of ARQ 087)

After written informed consent is obtained, the subject's eligibility for the study and baseline disease state will be assessed.

The following will be evaluated and documented within 21 days prior to the first dose of ARQ 087 (Day -21 – Day 0):

- Obtain written informed consent from the subject or subject's legal representative
- Medical history (see Section 6.1)
- Physical examination, including mucous membranes and skin (see Section 6.2)
- ECOG PS (see Appendix 2)
- Vital signs (height, weight, temperature, blood pressure, respiration rate, and pulse)
- Fasting clinical blood tests (see Section 6.4)\*

- Urinalysis (see Section 6.4)
- Serum pregnancy test, if applicable (see Section 6.4)
- 12-lead electrocardiogram (ECG) (see Section 6.3)
- Echocardiography or Multiple Gated Acquisition (MUGA) scan, if applicable (see Section 6.3)
- Blood samples for tumor markers, if applicable (to be tested at study site)
- Collect archival and/or fresh tissue biopsy samples (see Section 6.8)
  - For subjects enrolled in the Expanded Cohort, archival samples should be collected for all enrolled subjects, paired biopsy is optional. Both archival and pre-treatment fresh tumor samples should be collected prior to the first dose of the study drug
  - For subjects enrolled in the Food-effect Cohort, both archival and paired biopsy should be collected. If archival tissue is not available, paired fresh tumor biopsy should be performed to confirm the subjects' FGFR1-3 or KIT/PDGFR status.
- Record prior and concomitant medications (medications used within 30 days prior to the first dose of ARQ 087)
- Tumor measurement and staging [e.g., computed tomography (CT) scan, magnetic resonance imaging (MRI) or positron emission tomography (PET)] (see Section 6.7, Appendix 6) **Note:** CT, PET, and MRI scans can be used as a Baseline assessment if they were performed within four weeks (28 days) prior to the first dose of ARQ 087.

\* Fasting clinical blood tests obtained during the Pre-study Visit can be used for Day 1 if they are performed within 72 hours prior to the first dose of the study drug (Cycle 1, Day 1 visit).

Subjects who satisfy all inclusion and exclusion criteria may be enrolled in the study.

### **5.3 Treatment Period 1 (PK): Single-Dose Administration of ARQ 087; Cohorts 1-4**

The approximate duration of Treatment Period 1 will be 4 days.

#### **5.3.1 Day 1 (Day of the Single Dose of ARQ 087 Administration)**

The following assessments will be made during this visit:

- Physical examination, including mucous membranes and skin
- ECOG PS
- Vital signs (temperature, blood pressure, respiration rate, and pulse)
- Fasting clinical blood tests (see Section 6.4)\*
- Blood sample for pharmacokinetics (see Section 6.5; blood samples will be collected immediately prior to the first dose of ARQ 087 and will continue through 72 hours after study drug administration.)
- Blood samples for pharmacodynamics (see Section 6.6)

- Tumor biopsy (if applicable, see Section 6.8)
- Record concomitant medications
- Administer a single dose of ARQ 087
- Assess adverse events (AE; after study drug administration)

\* If Baseline fasting clinical blood tests are obtained more than 72 hours prior to the first dose of ARQ 087, then Day 1 fasting clinical blood tests should be repeated, however, they may be obtained within 24 hours prior to the first dose of study drug.

### 5.3.2 Day 2 (24 Hours; $\pm$ 2 Hours, Post-Dose on Day 1)

The following assessments will be made during this visit:

- Vital signs (temperature, blood pressure, respiration rate, and pulse)
- Blood sample for pharmacokinetics (see Section 6.5)
- Blood samples for pharmacodynamics (see Section 6.6)
- Assess AEs
- Record concomitant medications

### 5.3.3 Day 3 (48 Hours; $\pm$ 2 Hours, Post-Dose on Day 1)

The following assessments will be made during this visit:

- Vital signs (temperature, blood pressure, respiration rate, and pulse)
- Blood sample for pharmacokinetics (see Section 6.5)
- Blood samples for pharmacodynamics (see Section 6.6)
- Assess AEs
- Record concomitant medications

### 5.3.4 Day 4 (72 Hours; $\pm$ 2 Hours, Post-Dose on Day 1)

The following assessments will be made during this visit:

- Vital signs (temperature, blood pressure, respiration rate, and pulse)
- Blood sample for pharmacokinetics (see Section 6.5)
- Blood samples for pharmacodynamics (see Section 6.6)
- Assess AEs
- Record concomitant medications

The washout time between Treatment Period 1 and Treatment Period 2 should be at least 72 hours. If the subject continues to be eligible, the treatment with ARQ 087 per the Treatment Period 2 schedule may be initiated immediately after the 72-hour PK sample is drawn.

## 5.4 Continuous Administration of ARQ 087: Dose Escalation/Food-effect Cohorts and Expanded Cohort

After completion of the Treatment Period 1 Day 4 (Cohorts 1-4) assessments or if the subject is enrolled in the Dose Escalation/Food-effect and Expanded cohorts, the subject will continue treatment according to the schedule of visits and assessments described below.

### 5.4.1 Cycle 1, Weekly Evaluations

#### 5.4.1.1 Week 1 (Day 1)

The following assessments will be made during this visit:

- Physical examination, including mucous membranes and skin
- ECOG PS
- Vital signs (weight, temperature, blood pressure, respiration rate and pulse)
- Fasting clinical blood tests (see Section 6.4)\*
- Urinalysis (see Section 6.4)
- Blood sample for pharmacokinetics (except Expanded Cohort, see Section 6.5)
- Blood samples for pharmacodynamics (see Section 6.6)
- Blood samples for tumor marker(s), if applicable (to be tested at the study site)
- 12-lead ECG (see Section 6.3)
- Record concomitant medications
- Dispense ARQ 087
- Assess AEs (after study drug administration)

\* Fasting clinical blood tests may be obtained within 24 hours of the visit.

#### 5.4.2 Week 2 (Day 8; $\pm$ 3 Days)

The following assessments will be made during this visit:

- Physical examination, including mucous membranes and skin
- ECOG PS
- Vital signs (temperature, blood pressure, respiration rate and pulse)
- Fasting clinical blood tests (see Section 6.4)\*
- Blood sample for pharmacokinetics (except Expanded Cohort, see Section 6.5)
- Blood sample for pharmacodynamics (except Expanded Cohort, see Section 6.6)
- Assess AEs
- Record concomitant medications
- Dispense ARQ 087

\* Fasting clinical blood tests may be obtained within 24 hours of the visit.

#### 5.4.3 Week 3 (Day 15; $\pm$ 3 Days)

The following assessments will be made during this visit:

- Physical examination, including mucous membranes and skin
- ECOG PS
- Vital signs (weight, temperature, blood pressure, respiration rate and pulse)
- Fasting clinical blood tests (see Section 6.4)\*
- Urinalysis (see Section 6.4)
- 12-lead ECG (see Section 6.3)
- Blood sample for pharmacokinetics (except Expanded Cohort, see Section 6.5)
- Blood sample for pharmacodynamics (except Expanded Cohort, see Section 6.6)
- Assess AEs
- Record concomitant medications
- Dispense ARQ 087

\* Fasting clinical blood tests may be obtained within 24 hours of the visit.

#### 5.4.4 Week 4 (Day 22; $\pm$ 3 Days)

The following assessments will be made during this visit:

- Physical examination, including mucous membranes and skin
- ECOG PS
- Vital signs (temperature, blood pressure, respiration rate and pulse)
- Fasting clinical blood tests (see Section 6.4)\*
- Blood samples for pharmacokinetics (except Expanded Cohort, see Section 6.5)
- Blood sample for pharmacodynamics (except Expanded Cohort, see Section 6.6)
- Tumor biopsy if applicable (see Section 6.8)
- Assess AEs
- Record concomitant medications
- Dispense ARQ 087

\* Fasting clinical blood tests may be obtained within 24 hours of the visit.

#### 5.4.5 Week 4 (Day 23; except Expanded Cohort)

The following assessments will be made during this visit:

- Vital signs (temperature, blood pressure, respiration rate and pulse)
- Blood sample for pharmacokinetics (see Section 6.5)

- Assess AEs
- Record concomitant medications

**Note:** Because the Cycle 1 Day 22 and Day 23 visits are days when the full PK is performed, subjects enrolled in **Cohort 1** (25 mg every other day) Cycle 1 Week 4 visits should be scheduled on the day of ARQ 087 administration and the next consecutive day, when drug is not taken, e.g., Cycle 1 Day 21 and Day 22 or Cycle 1 Day 23 and Day 24.

## 5.5 Cycle 2 and Following Cycles, Bi-weekly Evaluations

### 5.5.1 Week 1 (Day 1; $\pm$ 3 Days)

The following assessments will be made during this visit:

- Physical examination, including mucous membranes and skin
- ECOG PS
- Vital signs (weight, temperature, blood pressure, respiration rate and pulse)
- Fasting clinical blood tests (see Section 6.4)\*
- Blood samples for tumor marker(s), if applicable (to be tested at study site)
- Blood samples for pharmacokinetics (except Expanded Cohort, see Section 6.5)
- Blood samples for pharmacodynamics (see Section 6.6)
- Urinalysis (see Section 6.4)
- Tumor measurement and staging (see Section 6.7, Day 1 of every odd cycle or every 8 weeks, e.g. C3D1, C5D1, etc.)
- 12-lead ECG (see Section 6.3)
- Echocardiography or MUGA scan to measure LVEF, if applicable and clinically indicated (see Section 6.3)
- Assess AEs
- Record concomitant medications
- Dispense ARQ 087

\* Fasting clinical blood tests may be obtained within 24 hours of the visit.

### 5.5.2 Week 3 (Day 15; $\pm$ 3 Days)

The following assessments will be made during this visit:

- Physical examination, including mucous membranes and skin
- ECOG PS
- Vital signs (temperature, blood pressure, respiration rate and pulse)
- Fasting clinical blood tests (see Section 6.4)\*
- Blood samples for pharmacokinetics (except Expanded Cohort, see Section 6.5)

- Assess AEs
- Record concomitant medications
- Dispense ARQ 087

\* Fasting clinical blood tests may be obtained within 24 hours of the visit.

**Note:** Subjects who do not experience Grade 3/4 toxicity after four cycles (16 weeks) at the same dose level can be evaluated every four weeks (monthly) upon agreement between the Investigator and the ArQule Medical Monitor. The schedule of assessment should follow the Cycle 2 Week 1 schedule.

## 5.6 End of Treatment Visit (7 [+3] Days after the Last Dose of ARQ 087)

If possible, the End of Treatment Visit should be performed 7 [+3] days after the last dose of ARQ 087. The following assessments will be made during the End of Treatment Visit:

- Physical examination, including mucous membranes and skin
- ECOG PS
- Vital signs (weight, temperature, blood pressure, respiration rate, and pulse)
- Fasting clinical blood tests (see Section 6.4)
- Urinalysis (see Section 6.4)
- Serum pregnancy test, if applicable (see Section 6.4)
- 12-lead ECG (see Section 6.3)
- Echocardiography or MUGA scan to measure LVEF, if applicable (see Section 6.3)
- Blood samples for tumor marker(s), if applicable (to be tested at study site)
- Blood samples for pharmacokinetics (except Expanded Cohort, see Section 6.5)
- Tumor measurement and staging if not done within four weeks (28 days) prior to the end of treatment visit (see Section 6.7)
- AEs assessment
- Record concomitant medications

## 5.7 30-day ( $\pm$ 3 Days) Safety Follow-Up Visit

All subjects will be followed for a minimum of 30 days after the last dose of ARQ 087. If a subject is removed from the study treatment due to drug-related AEs, the subject will be followed until drug-related AEs occurring during the study or within 30 days after the last dose of ARQ 087 have resolved to baseline, CTCAE Grade 1, stabilized, or are deemed irreversible. If a subject receives other anticancer therapy within the 30-day follow-up period, the follow-up for AEs will cease, beginning the first day of the new therapy.

**Note:** The visit can be done either as an office visit or over the telephone.

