## 5.8 Discontinuation from the Treatment/Study

Subjects will be removed from the study treatment at any time if they meet any of the following criteria:

- Documented radiographic or clinical progression of disease\*
- Noncompliance with any part of the study, as evaluated by the Investigator and Medical Monitor
- Clinically unacceptable toxicities despite optimal treatment or dose reduction
- Withdrawal of consent
- Investigator's decision (in agreement with the Sponsor/Medical Monitor or designee)
- Lost to Follow-up
- Death

\* Subjects may remain on treatment if, in the opinion of the Investigator and with the agreement of ArQule's Medical Monitor, they continue to derive benefit from the treatment.

Subjects will be removed from the study if they meet any of the following criteria:

- Safety follow-up visit is completed per protocol and drug-related AEs have resolved to baseline, CTCAE Grade 1, stabilized, or are deemed irreversible.
- Withdrawal of consent
- Lost to Follow-up
- Death

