## 8.5 Post-Treatment Safety Follow-up

In this study, the post-treatment safety follow-up period is defined as 30 days after the last dose of assigned treatment. All AEs occurring during the study period from the time of the first dose of study drug administration to the last day of the 30-day post-treatment follow-up period will be captured.

All subjects will be followed for a minimum of 30 days after discontinuation of the study drug. All subjects should be instructed to reported AEs or SAEs occurring during the 30-day post-treatment safety follow-up period.

Unresolved study drug related (see Section 8.1.6 for definition) AEs and SAEs at the time of treatment discontinuation or new study drug related AEs and SAEs that occur during the 30-day safety follow-up period will be followed until they have, in opinion of the Investigator, resolved to baseline, have stabilized, or are deemed to be irreversible.

If a subject receives other anticancer therapy within the 30-day follow-up period, the follow-up for AEs will cease, beginning the first day of the new therapy.

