5.4.7 Analyses of Safety Variables

All analyses for the safety variables will be performed on safety population. Safety variables include adverse events, laboratory parameters, vital signs, ECOG performance status, 12-lead ECG and physical exams.

Descriptive statistics will be calculated for quantitative safety data, frequency counts and percentages will be compiled for classification of qualitative safety data. All percentages will be calculated based on the number of subjects in the safety population, unless otherwise indicated. Baseline is defined as the last non-missing value prior to the first dose date or on day 1, unless otherwise noted.

Adverse Events

Adverse events will be evaluated for severity using NCI-CTCAE, version 4.03. AE summaries will include treatment-emergent adverse events (TEAEs).

A TEAE is defined as:

- an AE which is not present prior to the first dose of ARQ 087 and started after taking the study drug during the treatment period or within 30 days after the last dose of the study drug;
- an AE which is present prior to the first dose of ARQ 087 and increased in severity after taking study drug during the treatment period or within 30 days after the last dose of study drug;
- an AE which is considered study drug-related regardless of the start date of the event.

All TEAEs will be coded using Medical Dictionary for Regulatory Activities (MedDRA[®]) Version 15.1 and summaries will be presented by system organ class and preferred term. Separate TEAE summaries will be generated for the following categories:

- All TEAEs
- Severe TEAEs (Grade 3 or higher)
- SAEs
- TEAEs related to study drug
- TEAEs leading to treatment discontinuation
- TEAEs leading to treatment interruption
- TEAEs leading to treatment interruption then dose reduction
- TEAEs resulting in death
- TEAEs listed according to maximum severity
- TEAEs classified as DLTs

TEAEs will be summarized by presenting the number and percentage of subjects having at least one TEAE in each system organ class and preferred term. A subject with multiple occurrences of the same TEAE will be counted only once in the AE category.

Separate TEAE summaries will be presented by system organ class, preferred term, and maximum CTCAE 4.03 grade. A subject with multiple CTCAE grades for the same TEAE will be summarized under the maximum CTCAE grade recorded for the event.

Laboratory Test

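### The last scheduled adverse-event assessment may be held on Day 27, short of both the 30-day follow-up minimum and the 30-day TEAE window

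*Protocol*

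**What the plan says.** **Length of follow-up.** Protocol 5.7 says: "All subjects will be followed for a minimum of 30 days after the last dose of ARQ 087". Protocol 8.5 says: "All subjects will be followed for a minimum of 30 days after discontinuation of the study drug". It also states that "the post-treatment safety follow-up period is defined as 30 days after the last dose of assigned treatment". On capture, 8.5 covers "All AEs occurring during the study period from the time of the first dose of study drug administration to the last day" of that 30-day period.

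**Visit window.** The heading of Protocol 5.7 places the visit at 30 days plus or minus 3 days and a note allows it by telephone. All three Appendix 1 schedules (Cohorts 1-4; Cohorts 5-10 and Food-effect; Expanded Cohort) print the same two-sided window, with this visit as the last column. SAP Tables 3 and 4 also print plus or minus 3 days. SAP Table 2, for Cohorts 1-4, reads +3 days.

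**Leaving the study.** The relevant criterion in Protocol 5.8 is: "Safety follow-up visit is completed per protocol and drug-related AEs have resolved to baseline, CTCAE Grade 1, stabilized, or are deemed irreversible". It does not mention Day 30.

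**Analysis.** SAP 5.4.7 treats an event not present before the first dose as treatment-emergent if it "started after taking the study drug during the treatment period or within 30 days after the last dose of the study drug". Percentages are based on the safety population unless otherwise indicated.

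**The concern.** The window is two-sided but the requirement is a minimum. A site can hold the visit on Day 27, within the window, and the last planned question about adverse events is then asked before the period being counted has ended. An event or death on Day 29 meets the SAP's TEAE definition, but nothing scheduled would find it.

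Safety and tolerability is the primary objective of both parts of the study, and the TEAE tables are a main summary of it. The SAP has no rule for subjects whose last assessment came before Day 30, so they enter the percentages in the same way as subjects assessed at Day 30 or later. New drug-related events arising in the 30 days must also be followed under 8.5, which depends on their being detected.

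**Working it through.** The plan states no figure to reproduce. The check is date arithmetic plus a reading of the exit rule. Days are counted from the last dose.

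**Inputs**
- Nominal visit day 30, tolerance 3 days either side (Protocol 5.7 heading; Appendix 1).
- Minimum follow-up 30 days (Protocol 5.7 and 8.5).
- TEAE window 30 days after the last dose (SAP 5.4.7).
- Half-life about 1 week (Protocol 4.1.1), used for context only.

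**Step 1: earliest visit within the window.** 30 - 3 = Day 27. Latest: 30 + 3 = Day 33.

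**Step 2: days in the TEAE window after the last scheduled assessment.** Gap = max(0, 30 - visit day).

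| Visit day | Days without a scheduled assessment | Share of 30 days |
|---|---|---|
| 27 | 3 | 3/30 = 10% |
| 28 | 2 | 2/30 = 6.7% |
| 29 | 1 | 1/30 = 3.3% |
| 30 to 33 | 0 | 0% |

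**Step 3: who is exposed.** Protocol 5.8 sets a joint condition: the visit is completed and drug-related events have resolved, stabilized or been judged irreversible. A subject with an unresolved drug-related event is followed longer. Under 5.7 and 8.5, adverse-event follow-up stops for anyone who starts other anticancer therapy. The gap therefore concerns subjects seen on Days 27 to 29 with no unresolved drug-related event and no new anticancer therapy. The documents do not say how many that would be.

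**Step 4: what still covers those days.** Protocol 8.2 obliges investigators to capture events through the 30-day period, and 8.5 has subjects told to report them. Neither provision attaches a contact after the visit.

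**Step 5: with a 0/+3 window.** The earliest visit is Day 30, so the gap is max(0, 30 - 30) = 0 days.

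**Context.** Assuming simple mono-exponential decline with a 7-day half-life, the fraction of the end-of-treatment level left is 2^(-27/7) = 6.9% at Day 27 and 2^(-30/7) = 5.1% at Day 30. Some drug is still present, but this gives no event rate for those days.

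**The case against.** The strongest reply is that a visit window and a follow-up period are different things. The tolerance governs when the call is made, and the 30-day minimum governs adverse-event follow-up. A site can telephone on Day 27 and go on recording reports to Day 30, as 8.2 and 8.5 require. Serious events must be reported within 24 hours of knowledge whenever they become known. The exit rule in 5.8 refers to a visit completed per protocol, which can be read to include the protocol's own 30-day minimum. Two of the Appendix 1 schedules mark the visit as approximately 30 days, which suggests that the looseness was intended.

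Much of this stands, and it rules out several stronger readings:

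- A reader might infer that events on Days 28 to 30 will be lost, or that no one is responsible for them. They are at risk of being missed; the duty to capture them remains.
- A reader might infer that using the window necessarily breaches the 30-day minimum. It does so only if follow-up actually ends with the visit, which 5.8 permits on one reading but does not require.
- A reader might infer that completing the visit alone releases the subject. The condition on drug-related events must also be met.
- A reader might infer that TEAEs are a designated primary endpoint, or that the SAP certifies these subjects as completely followed. The documents name safety and tolerability as the primary objective, list several safety variables without ranking them, and define no follow-up-completeness status.
- A reader might infer from SAP Table 2 that the SAP deliberately chose a one-sided window for Cohorts 1-4. The difference is one character in a table read by a program, and the plus sign may be a plus-or-minus sign that lost its lower stroke. The argument does not use it.

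The reply does not remove the mismatch. General duties and self-report are weaker than a check made once the counted period has ended, and the text of 5.8 leaves the exit date open.

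**Conclusion.** The point holds as a small inconsistency. The last scheduled adverse-event assessment may fall up to 3 days before the end of the period that the protocol promises to follow and the SAP counts. For subjects seen on Days 27 to 29 with no unresolved drug-related event, 5.8 permits exit without requiring Day 30 to have passed.

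The loss of scheduled observation is at most 3 of 30 days (10%) for a subject seen on Day 27, less for Days 28 and 29, and nil from Day 30. Any resulting error is an under-count. The number of events affected cannot be estimated, because the documents give neither the distribution of visit days nor a late event rate. No effect on a study conclusion is shown. The conclusion assumes that the two-sided window in the protocol is as printed and that 5.8 is applied as worded.

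**What to change.** - Set the window for this visit to 0/+3 days (not before Day 30) in Protocol 5.7, all three Appendix 1 schedules, and SAP Tables 3 and 4. Remove the approximate sign from the two Appendix 1 column headings that carry it.
- Check SAP Table 2 against the source file and confirm that it shows the same window.
- State in Protocol 5.8 that exit through the safety follow-up criterion requires Day 30 to have passed.

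A one-sided window already has a precedent in this protocol: the End of Treatment visit is set at 7 days with +3 only. The cost is a wording change and slightly less scheduling freedom for sites, eased by the telephone option. No dose or treatment rule is affected.
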